**Table 2. Clinical criteria for diagnosing anaphylaxis for use in primary analysis**

Anaphylaxis is highly likely when any of the following 3 criteria are fulfilled:

1. Acute onset of an illness (minutes to several hours) with involvement of the skin, mucosal tissue, or both (e.g., generalized hives, pruritus or flushing, swollen lips-tongue-uvula) AND AT LEAST ONE OF THE FOLLOWING:
 
 
a. Respiratory compromise (e.g., dyspnea, wheeze-bronchospasm, stridor, reduced peak expiratory flow, hypoxemia)
 
b. Reduced blood pressure or associated symptoms of end-organ dysfunction (e.g., hypotonia [collapse], syncope, incontinence)
 

2. Two or more of the following that occur rapidly after exposure to a likely allergen for that patient (minutes to several hours):
 
 
a. Involvement of the skin-mucosal tissue (e.g., generalized hives, itch-flush, swollen lips-tongue uvula)
 
b. Respiratory compromise (e.g., dyspnea, wheeze-bronchospasm, stridor, reduced peak expiratory flow, hypoxemia)
 
c. Reduced blood pressure or associated symptoms (e.g., hypotonia [collapse], syncope, incontinence)
 
d. Persistent gastrointestinal symptoms (e.g., crampy abdominal pain, vomiting)
 

3. Reduced blood pressure after exposure to known allergen for that patient (minutes to several hours):
 
 
a. Infants and children: low systolic blood pressure (age specific) or greater than 30% decrease in systolic blood pressure*
 
b. Adults: systolic blood pressure of less than 90 mm Hg or greater than 30% decrease from that person's baseline blood pressure
 

**Anaphylaxis is highly likely when any of the following 3 criteria are fulfilled:**

\*Low systolic blood pressure for children is defined as less than 70 mm Hg from 1 month to 1 year, less than (70 mm Hg + [2 x age]) from 1 to 10 years, and less than 90 mm Hg from 11 to 17 years.

For secondary analyses, clinician adjudicators will divide all potential case as (1) not a hypersensitivity reaction; (2) mild hypersensitivity; (3) moderate hypersensitivity; or (4) severe hypersensitivity, using the classification system developed by Brown *et al.* in 2004 (Table 3). We will use moderate and severe allergic reactions as a separate outcome variable in secondary analysis.

**Table 3. Grading system for generalized hypersensitivity reactions for use in secondary analysis**

Grade	Defined by
1 – Mild (skin and subcutaneous tissues only)*	Generalized erythema, urticaria, periorbital edema, or angioedema
2 – Moderate (features suggesting respiratory, cardiovascular, or gastrointestinal involvement)	Dyspnea, stridor, wheeze, nausea, vomiting, dizziness, or abdominal pain
3 – Severe (hypoza, hypotension, or neurologic compromise)	Cyanosis or SpO 2 ≤ 92% at any stage, hypotension (systolic blood pressure < 90 mm Hg in adults), confusion, collapse, loss of consciousness, or incontinence

\*Mild reactions can be further subclassified into those with and without angioedema (see text).

**E. IDENTIFICATION OF COVARIATES**

Table 4 lists the covariates the workgroup will obtain from the 183-day period preceding (and including) the index date. Age on index date and gender will be identified from the MSDD’s demographic files. Diagnostic codes recorded during inpatient, outpatient, or emergency department encounters will be obtained from the MSDD’s diagnosis file.

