### **B. IDENTIFICATION OF NEW-USERS OF DRUGS OF INTEREST**

We propose to use a “new-user” cohort design. We will identify health plan members with a first administration of a parenteral iron preparation during the period January 1, 2000 to June 30, 2013. We note that not all Data Partners will have data for the entire study period. Use of parenteral iron preparations will be identified using the procedure codes shown in Table 1. We will not identify parenteral iron administration using the National Drug Codes (NDCs), because in a summary table analysis we found the use of IV iron products identified as by NDCs in the Mini-Sentinel Distributed Database to be quite low (~3,000 vs. ~200,000 identified by procedure codes, see Section H). Given that anaphylaxis is a rare event, we decided that this number is too low to identify an adequate number of events among users.

We refer to the procedure date of the first administration of the iron preparation as the *index date*. We will require eligible individuals to meet all of the following criteria during the 183-day period prior to the index date: 1) continuous health plan enrollment with pharmacy and medical benefits; and 2) no administration of any of the parenteral iron products of interest in the emergency department, outpatient (ambulatory) visits, or inpatient visits; and (3) no procedure codes for dialysis (Appendix 1). Dialysis patients were excluded from analysis because they represent less than half of the population receiving parenteral iron in the MSDD, their prescribing patterns appear different from other parenteral iron users, and because dialysis patients may be clinically distinct from other parenteral iron users. Gaps of 45 days or less in enrollment will be ignored because they usually represent administrative gaps rather than actual disenrollment.

The exposure group will be new users of iron dextran. The comparison group will be new users of other parenteral iron products. We will identify use of iron preparations in the inpatient, emergency department, and outpatient settings, although we expect the majority of parenteral iron use to be in the outpatient setting. For patients who may be eligible for more than one new use episode during the study period, only their first eligible episode will be included in the analysis.

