### **C. IDENTIFICATION OF OUTCOME OF INTEREST**

We will employ the algorithm developed by the Mini-Sentinel Anaphylaxis Validation Workgroup to identify potential cases of anaphylaxis using health plan data (Appendices 2 and 3). We will identify cases of potential anaphylaxis occurring on the day of or the day after exposure to parenteral iron. Because we expect that the number of cases identified will be small, we will further include a more sensitive algorithm that will identify patients who received epinephrine the same day or the day after being administered parenteral iron. We will review these epinephrine cases using the same methods as anaphylaxis cases. Chart abstractors and adjudicators will be blinded to whether cases were identified using the anaphylaxis algorithm or from epinephrine administration.

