\*For history of anaphylaxis not related to food, oral steroid use, injectable steroid use, drug allergy, other allergy, food/insect/latex allergy identify codes found within 183 days preceding the index date, but not including the index date.

† Define use as a dispensing (fill) in the outpatient pharmacy dispensing file for 183 days preceding and including the index date

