**F. FOLLOW-UP**

Follow up will begin on the index date, and end on the first occurrence of anaphylaxis or one day after the index date, whichever occurs first.

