**Table 5. Baseline characteristics**

	Iron dextran N (%)	Other parenteral iron products N (%)
Age on index date 0-4 years 5-18 years 19-44 years 45-64 years 65 and older		
Gender Female Male		
History of anaphylaxis, not related to food		
Drug allergy		
Atopic dermatitis		
Food, latex, insect bite allergy		
Other allergy		
Allergic rhinitis		
Asthma		
HIV infection		
COPD		

	Iron dextran N (%)	Other parenteral iron products N (%)
Coronary heart disease		
Hypertension		
Immunosuppressive therapy		
Oral steroid use		
Injectable steroid use		
Antibiotic use		
Beta blocker use		
ACE inhibitor use		
ARB use		
Year of new use		
2000		
2001		
2002		
2003		
2004		
2005		
2006		
2007		
2008		
2009		
2010		
2011		
2012		

	Iron dextran N (%)	Other parenteral iron products N (%)
2013		
Clinical setting where IV iron is administered* Outpatient Inpatient Emergency department		

\* Use on the index date; for patients receiving IV iron in more than one clinical setting on the index date, report use in each setting for which it is documented

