## 5. Analysis comparing risk of anaphylaxis between parenteral iron dextran and other iron products

### a. Estimation of relative risk

We will employ two propensity score-based approaches – matching and stratification – to investigate the association between the use of iron dextran and anaphylaxis, with use of other parenteral iron products as the comparison group. We will assess the covariate balance after matching and stratification. The propensity score is defined as the probability of receiving iron dextran given the measured confounders. We use the propensity score methods as our primary approach because the number of anaphylaxis events is expected to be small and the number of confounders is relatively large. The propensity score approach overcomes this issue by allowing us to adjust for all measured confounders simultaneously through a composite summary score. We will estimate the propensity scores by site using a logistic model common to all Data Partners using the probability of receiving iron dextran as the dependent variable and covariates in Table 5 as independent variables.

Propensity score matching will be conducted within sites. We will match one iron dextran user with one other iron product user using 1:1 nearest-neighbor matching without replacement

with a caliper of 0.05. Unmatched patients will be excluded from subsequent analyses. Each Data Partner will transfer an aggregated dataset of the matched cohort, which includes only the number of users and outcome events in each treatment group, to the project team. The project team will then estimate the odds ratio of the confirmed anaphylactoid/anaphylaxis event, from the Sampson criteria, comparing iron dextran users with other iron product users. The aggregated dataset will only include the number of users and outcome events within each treatment group. By matching one iron dextran user with one other iron product user with similar propensity score, we estimate the average treatment effect among the treated (ATT). Thus, we will also do propensity score stratification to estimate the population-wide average treatment effect (ATE).

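### Asthma, COPD, coronary heart disease and possibly allergic rhinitis are read on the index date, when the outcome can already have occurred, so a reaction-day code can enter the propensity score as a baseline value

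*Protocol*

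**What the plan says.** Section II.B fixes day 0 as the calendar date on which iron was first given: "We refer to the procedure date of the first administration of the iron preparation as the" index date.

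Section II.E sets the default look-back for covariates: "Table 4 lists the covariates the workgroup will obtain from the 183-day period preceding (and including) the index date". Diagnoses are drawn from inpatient, outpatient and emergency encounters. No rule orders events within a day.

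The asterisk footnote to Table 4 makes an exception for six rows: non-food anaphylaxis history, drug allergy, food/insect/latex allergy, other allergy, oral steroids and injectable steroids. For these the rule is to "identify codes found within 183 days preceding the index date, but not including the index date". (The two steroid rows also carry the dagger, which includes the index date. That conflict is a separate matter.) Asthma, COPD, coronary heart disease, allergic rhinitis, atopic dermatitis, primary hypertension and HIV have no asterisk, so the default applies to them.

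On the outcome, Section II.C says: "We will identify cases of potential anaphylaxis occurring on the day of or the day after exposure to parenteral iron". Section II.F agrees: "Follow up will begin on the index date, and end on the first occurrence of anaphylaxis or one day after the index date", whichever is first.

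Section II.G.5.a estimates the propensity score with "covariates in Table 5 as independent variables". Table 5 contains all the unasterisked diagnoses. The score determines both the 1:1 matching and the site-specific quintiles.

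**The concern.** A baseline covariate should be fixed before the outcome can occur. Here four diagnosis rows can be filled by the encounter that treats the outcome. Table 2 makes dyspnea, wheeze-bronchospasm and hypoxemia defining features of anaphylaxis and requires onset within hours, so most true reactions would be expected on day 0. If the treating clinician codes wheeze as 493 or chest pain as 413, that patient becomes asthma-positive or coronary-positive at baseline because of the reaction.

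The effect on the analysis is direct. With few cases among about 100,000 users, the fitted propensity model hardly changes, but the affected case gets a different score. It then falls in a different stratum or draws a different match. The covariate error therefore depends on the outcome, and it sits in the primary analysis. Chart review under Section II.D adjudicates the outcome and is not planned to correct covariates. The asterisk shows that the protocol keeps day 0 out of the rows closest to an allergic reaction. It stops short of rows whose codes share features with the outcome.

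**Working it through.** **Step 1. Compare the windows.**

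| Item | Days relative to index date | Source |
|---|---|---|
| Unasterisked diagnoses | -183 to 0 | Section II.E |
| Asterisked rows | -183 to -1 | Table 4 footnote |
| Outcome | 0 to +1 | Sections II.C, II.F |

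The unasterisked rows share day 0 with the outcome. The asterisked rows share no day with it.

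**Step 2. Which unasterisked rows could a reaction fill?** Asthma, COPD and coronary heart disease (413 includes angina) plausibly could, and allergic rhinitis possibly. HIV, atopic dermatitis and primary hypertension are not plausible consequences of a reaction.

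**Step 3. Inputs for an illustration.** From Section II.G.7: 40,015 dextran and 60,714 other users, 100,729 in all. From the first row of Table 7: baseline risk 2.05 per 10,000, relative risk 2.80, stated power 81.3%. A continuity-corrected arcsine approximation to Fisher's exact test (two-sided 0.05) gives 80.6%, and all 12 rows fall within 0.7 points of the stated power. The inputs are therefore read correctly. The present point rests on no stated power figure.

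Expected cases: 40,015 × 0.000205 × 2.80 = 23.0 dextran and 60,714 × 0.000205 = 12.4 other, about 35 in all.

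Assumed, because the documents give no figure:
- flag prevalence of 5% or 10%;
- flag-dextran odds ratio g of 0.5, 0.7, 1.0 or 1.5;
- share f of unflagged cases gaining the flag on day 0 of 10% or 30%, equal in both groups;
- one pooled site, two strata (flag yes or no), and no effect of the flag on risk.

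**Step 4. Formula.** Mantel-Haenszel odds ratio = Σ(aᵢdᵢ/Tᵢ) / Σ(bᵢcᵢ/Tᵢ), where a and c are cases on dextran and other iron, b and d are the corresponding non-cases, and T is the stratum total.

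**Step 5. Worked case: prevalence 5%, g = 0.5, f = 30%.** Users are 38,737 dextran and 56,956 other unflagged, and 1,278 and 3,758 flagged.

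- Before any reaction-day coding, cases are 22.23 and 11.68 unflagged, 0.73 and 0.77 flagged. Odds ratio = (13.231 + 0.547) / (4.724 + 0.195) = 2.80.
- 30% of unflagged cases move: 6.67 dextran and 3.50 other. Cases are now 15.56 and 8.17 unflagged, 7.40 and 4.27 flagged. Odds ratio = (9.263 + 5.513) / (3.307 + 1.082) = 3.37, or +20%.

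With g = 1.5 and the other inputs unchanged: (9.165 + 3.998) / (3.272 + 2.012) = 2.49, or -11%.

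**Step 6. Range.** Odds ratio, true value 2.80, at prevalence 5% (10% in brackets):

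| g | f = 10% | f = 30% |
|---|---|---|
| 0.5 | 2.98 (2.97) | 3.37 (3.34) |
| 0.7 | 2.89 (2.89) | 3.09 (3.08) |
| 1.0 | 2.80 (2.80) | 2.80 (2.80) |
| 1.5 | 2.69 (2.70) | 2.49 (2.51) |

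If the flag also doubles the risk of anaphylaxis, no entry changes by more than about 0.04. The matched analysis was not computed.

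**The case against.** The best defence is that these rows are chronic diseases. The infusion visit is a legitimate place to find them recorded, and dropping that day loses real information. The rows most likely to be filled by a reaction are already protected by the asterisk. Acute bronchospasm (519.11), stridor (786.1) and hypotension (458.9) have their own codes in Appendix 2, and none of these is a covariate. The route through 493 or 413 therefore needs miscoding or a true flare, and no frequency is given. The shift is also small beside random error: with 23.0 and 12.4 cases, the 95% interval spans a factor of about exp(1.96 × √(1/23.0 + 1/12.4)) = 1.99 each way. None of the illustrated values reaches the relative risk of four that Section II.G.7 treats as decision-relevant.

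This stands as a limit on size. Consequences of a reaction can enter the score, and nothing shows that many do. It does not remove the overlap, and sampling error is no reason to keep an avoidable error that depends on the outcome.

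Three stronger readings are tempting, and the documents do not support them.

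- *That the infusion setting is contaminated in the same way.* Table 4 defines setting by where the iron was given, and the Table 5 footnote says "for patients receiving IV iron in more than one clinical setting on the index date, report use in each setting for which it is documented". Iron given in a clinic stays clinic iron if the patient is then sent to the emergency department. Contamination would need claims to be merged across encounters, which the protocol does not describe.
- *That the odds ratio is pushed upward.* Section II.H.2 says only that avoidance of dextran in patients thought to be at high risk is possible, and it names none of these diagnoses. Step 6 shows shifts in both directions and none.
- *That only cases can gain a flag this way.* A reaction that fails the Table 2 criteria is a non-case in the primary analysis, yet may involve wheeze or dyspnea (Table 3, moderate). The algorithm's predictive value of 63.1%, cited in Section I.C, suggests that such events will occur. Their numerical effect is small.

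**Conclusion.** The point holds for asthma, COPD and coronary heart disease, and possibly for allergic rhinitis. The protocol fixes a covariate window that overlaps the outcome window on day 0 and feeds these rows into the primary propensity score. This is a stated rule that is badly set, and not a detail left open for an analysis plan.

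The size and direction are unknown. Under the stated assumptions, the stratified odds ratio moves by about +3% to +20% for flag-dextran odds ratios of 0.7 to 0.5 and by about -3% to -11% at 1.5. It does not move at 1.0, nor if no case is coded this way. The share of cases affected, the flag prevalence and the flag-dextran odds ratio all come from outside the documents. The correction is worth making because it is cheap and removes an outcome-dependent error. The documents do not show that the result would be materially wrong without it.

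**What to change.** Add the asterisk to asthma, COPD, coronary heart disease and allergic rhinitis in Table 4, and name these rows in the asterisk footnote, so that their window is days -183 to -1. Qualify the default window in Section II.E to match. Applying the rule to atopic dermatitis, hypertension and HIV would serve uniformity only. The definition of clinical setting needs no change on this ground.

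The cost is one footnote and one query parameter. A few chronic diagnoses first coded at the infusion visit will be lost. No stated sample size or power figure changes.

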**Table 4. ICD-9-CM codes to identify covariates**

Confounder	Categorization	Identified by ICD-9-CM code(s) (unless otherwise noted)
History of anaphylaxis, not related to food*	Yes/No	995.0, 999.4, V13.81
Drug allergy*	Yes/No	995.27, V15.08, V14
Atopic dermatitis	Yes/No	691.8
Food/insect/latex allergy*	Yes/No	V15.01, V15.02, V15.03, V15.04, V15.05, V15.06, 995.6, V15.07
Other allergy*	Yes/No	995.3, 518.6, 558.3, 708, V15.09
Allergic rhinitis	Yes/No	477
Asthma	Yes/No	493
HIV infection	Yes/No	V08, 042
Chronic obstructive pulmonary disease (COPD)	Yes/No	491, 492, 496
Coronary heart disease	Yes/No	413, 414
Primary hypertension	Yes/No	401
Immunosuppressive therapy	Yes/No	Outpatient pharmacy dispensing file using National Drug Codes and procedure file for identifying HCPCs codes for selected immunosuppressives (alefacept, azathioprine, basiliximab, belatacept, non-ophthalmic cyclosporine, glatiramer, mycophenolate, sirolimus, and non-topical tacrolimus), selected

Confounder	Categorization	Identified by ICD-9-CM code(s) (unless otherwise noted)
		immunomodulators (abatacept, adalumumab, anakinra, canakinumab, certolizumab, dimethyl fumarate, etanercept, fingolimod, golimumab, infliximab, lenalidomide, mitoxantrone, natalizumab, pomalidomide, rilonacept, teriflunomide, thalidomide, tocilizumab, and ustekinumab), a selected antirheumatic kinase inhibitor (tofacitinib), selected monoclonal antibodies (alemtuzumab, ofatumumab, and rituximab), or an alkylating agent (cyclophosphamide)
Oral steroid use* †	Yes/No	Outpatient pharmacy dispensing file using National Drug Codes
Injectable steroid use* †	Yes/No	Outpatient pharmacy dispensing file using National Drug Codes and procedure file for identifying HCPCs codes
Antibiotic use †	Yes/No	Outpatient pharmacy dispensing file using National Drug Codes
Beta blocker use †	Yes/No	Outpatient pharmacy dispensing file using National Drug Codes
ACE inhibitor use †	Yes/No	Outpatient pharmacy dispensing file using National Drug Codes
ARB use †	Yes/No	Outpatient pharmacy dispensing file using National Drug Codes
Year of new use	Number	n/a
Clinical setting where IV iron administered	Inpatient, outpatient, emergency	n/a

Confounder	Categorization	Identified by ICD-9-CM code(s) (unless otherwise noted)
	department	

\*For history of anaphylaxis not related to food, oral steroid use, injectable steroid use, drug allergy, other allergy, food/insect/latex allergy identify codes found within 183 days preceding the index date, but not including the index date.

† Define use as a dispensing (fill) in the outpatient pharmacy dispensing file for 183 days preceding and including the index date

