## H. POTENTIAL LIMITATIONS AND ATTEMPTS TO MINIMIZE THEM

### 1. Misclassification bias

Bias could be introduced by the misclassification of the exposure, parenteral iron, or the outcome, anaphylaxis. We will review all cases meeting criteria for anaphylaxis or identified with an administration of epinephrine to minimize misclassification while at the same time using a sensitive measure for more complete capture of cases. We will have two adjudicators independently review all potential cases of anaphylaxis to reduce misclassification of the outcome. This will reduce potential false positives but will not address false negatives. Adjudicators will be blinded to the specific parenteral iron product used. For the exposure of interest, iron dextran, we expect there will be some unavoidable grouping of high molecular weight and low molecular weight forms. However, since the literature indicates that these forms are often confused and substituted in clinical practice, it seems necessary to combine them in our study. As a result, we will not be able to estimate the risk of anaphylaxis separately for high and low molecular weight iron dextran. We will review each chart where the patient developed anaphylaxis in an attempt to ascertain whether the iron dextran agent involved was INFeD or Dexferrum. In addition, for all cases of anaphylaxis we will collect information about whether the patient received premedication (e.g., diphenhydramine, IV fluids, or corticosteroids) and, if so, which medications were used.

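### The two footnotes on the steroid rows of Table 4 give incompatible index-date windows, and one of them can let treatment of the reaction into the propensity score

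*Protocol*

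**What the plan says.** Section II.E sets the general rule: "Table 4 lists the covariates the workgroup will obtain from the 183-day period preceding (and including) the index date". Table 4 then marks some rows with footnotes.

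- The asterisk footnote names its variables, among them "oral steroid use, injectable steroid use, drug allergy, other allergy", and instructs sites to "identify codes found within 183 days preceding the index date, but not including the index date".
- The dagger footnote names no variable. It applies wherever the symbol stands: "Define use as a dispensing (fill) in the outpatient pharmacy dispensing file for 183 days preceding and including the index date".

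The rows "Oral steroid use" and "Injectable steroid use" carry both symbols. The other dagger rows (antibiotic, beta blocker, ACE inhibitor and ARB use) carry the dagger alone.

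On data source, the cell for oral steroids names the outpatient dispensing file. The cell for injectable steroids gives "Outpatient pharmacy dispensing file using National Drug Codes and procedure file for identifying HCPCs codes".

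Both steroid variables appear in Table 5, and Section II.G.5 puts the Table 5 covariates into the site-level propensity models. Section II.F starts follow-up on the index date and ends it no later than the next day. Section II.H.1 plans to record, for anaphylaxis cases, "whether the patient received premedication (e.g., diphenhydramine, IV fluids, or corticosteroids" and similar agents were given.

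**The concern.** A baseline covariate should be fixed before the outcome can occur. Here the risk window is the index date and the following day, so index-day records may arise before the infusion, during it, or after a reaction. The asterisk keeps the index date out for the variables that a reaction could most easily contaminate: anaphylaxis history, allergy codes and steroids. The dagger brings it back for steroids.

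If a steroid given or filled because of a reaction is coded as prior steroid use, the propensity score contains a consequence of the outcome, and cases move into different score regions because they are cases. The definition must be settled before sites run their models: they return only counts of users and events (by stratum for the stratified analysis), so the project team could not detect or undo the choice from the transferred data.

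**Working it through.** **1. The rules side by side**

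| Rule | Index date | Source |
|---|---|---|
| General rule, Section II.E | included | none fixed for steroids |
| Asterisk (names both steroid variables) | excluded | no file named |
| Dagger (attached to both steroid rows) | included | outpatient pharmacy fills only |
| Oral steroid cell | not stated | outpatient dispensing file |
| Injectable steroid cell | not stated | outpatient dispensing file plus HCPCS procedure codes |

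On the window, asterisk and dagger contradict each other for both rows. On the source, the conflict is between the dagger and the injectable cell. The oral cell agrees with the dagger.

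**2. What index-day data could enter under each reading**

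- Asterisk window: none.
- Dagger read literally: only outpatient fills dated on the index date, such as an oral premedication fill or a prescription filled after a reaction. Steroids given at the infusion visit, in the emergency department or in hospital would generally not be captured.
- Dagger window combined with the injectable cell's source: administered steroids with an HCPCS code on the index date as well, whether premedication or treatment.

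Claims carry a date rather than a clock time, so same-day premedication and treatment generally cannot be told apart.

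**3. Can this move the odds ratio?**

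The Protocol gives no figure to reproduce here. The following is an illustration.

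Inputs from the Protocol: 40,015 dextran and 60,714 other users (Section II.G.7); baseline risk 2.05 per 10,000 and relative risk 2.80 (first row of Table 7).

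Assumptions not in the Protocol: true prior steroid use of π1 (dextran) and π0 (other), unrelated to anaphylaxis risk; a share f of cases without prior use becomes flagged only because the reaction was treated. The analysis is a Mantel-Haenszel odds ratio stratified on the steroid flag alone.

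Expected cases: 40,015 × 0.000205 × 2.80 = 22.97 dextran; 60,714 × 0.000205 = 12.45 other. The share of cases flagged is π + f(1 − π).

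For π1 = 0.30, π0 = 0.20, f = 0.50:

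- Flagged cases: 22.97 × (0.30 + 0.35) = 14.93 dextran; 12.45 × (0.20 + 0.40) = 7.47 other. Flagged non-cases: 11,997.6 and 12,140.3. Stratum odds ratio = (14.93 × 12,140.3) / (11,997.6 × 7.47) = 2.02.
- Unflagged cases: 8.04 and 4.98. Non-cases: 27,994.4 and 48,561.2. Stratum odds ratio = 2.80.
- Mantel-Haenszel: (7.502 + 5.098) / (3.708 + 1.820) = 2.28.

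Other settings:

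| π1 vs π0 | f = 0 | f = 0.25 | f = 0.50 | f = 0.90 |
|---|---|---|---|---|
| 20% vs 20% | 2.80 | 2.80 | 2.80 | 2.80 |
| 30% vs 20% | 2.80 | 2.52 | 2.28 | 1.94 |
| 40% vs 20% | 2.80 | 2.33 | 1.96 | 1.50 |

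The direction follows the imbalance. In the flagged stratum the odds ratio is approximately 2.80 × [(π1 + f(1 − π1))/π1] / [(π0 + f(1 − π0))/π0]. With 20% dextran versus 30% other and f = 0.50 this is 2.80 × (0.60/0.20) / (0.65/0.30) = 3.88, so the bias would run upward.

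**The case against.** The best reply is that the text already shows which rule is meant. Section II.E sets a general window, the asterisk is an express exception naming both steroid variables, and the dagger is a generic definition of drug use shared with four other drug classes. A specific exception normally governs, so the dagger may be a leftover symbol. This is plausible, and it points to the same window as the fix. It does not remove the contradiction, because the dagger is also expressly attached to both rows and a programmer has no stated rule for choosing.

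Four stronger readings are tempting, and the Protocol does not support them.

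- A reader might infer that the footnotes also contradict each other on data source. The asterisk names no file, so they do not; the mismatch is between the dagger and the injectable cell.
- A reader might infer that the dagger by itself brings infusion-visit or emergency-department steroids into the score. Its wording limits it to outpatient fills; administered steroids enter only if its window is joined to the HCPCS source.
- A reader might treat premedication as just as inadmissible as treatment. Premedication precedes the infusion and may reflect perceived risk, which Section II.H.2 says may influence product choice, so it may be a confounder. Only treatment of the reaction clearly follows the outcome.
- A reader might infer a large loss of matched pairs. The Protocol gives no index-day steroid frequencies, and a bound from exact matching on one binary variable does not describe a caliper match on a composite score. The quintile stratification discards nobody for want of a match.

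It is also fair that Section II.G.5 specifies one model common to all Data Partners. Divergent site readings are therefore a possibility and not something the Protocol implies.

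**Conclusion.** The point stands in a limited form. The index-date contradiction for both steroid rows is certain from the text, as is the source mismatch for injectable steroids. Both variables feed the primary analysis, and one of the two stated windows overlaps the risk window, so this is more than a typographical matter.

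The effect on the odds ratio is conditional. It needs the dagger window to be the one applied, some cases to be flagged through treatment of the reaction, and steroid use to differ between the iron groups. Its size cannot be determined from the Protocol. The illustration, which stratifies on one flag and not on the full score, shows only that the effect can range from none to material under assumed inputs. The change should be made before sites run their models.

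**What to change.** Remove the dagger from the oral and injectable steroid rows of Table 4. The asterisk then governs, with a window of day -183 to day -1, and the sources are those in the cells: the dispensing file for oral steroids, and the dispensing file plus HCPCS procedure codes for injectable steroids. In the opening text of Section II.E, note that the asterisked variables are an exception to the general window. Keep the dagger for antibiotic, beta blocker, ACE inhibitor and ARB use.

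The cost is a footnote edit, one sentence, and a check that the common site program uses the same window. The downside is that steroid premedication recorded only on the index date is no longer adjusted for, although it may carry some confounding. Index-day steroid records can be reported descriptively by iron group, so that readers can judge how much this matters.
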